11.6 Appendix 6. Sample Storage and Destruction

When permitted by local regulations, any blood, biomarker, pharmacokinetic (PK) sample collected according to the Schedule of Activities (Section 1.3) can be analyzed for any of the tests outlined in the protocol and for any tests necessary to minimize risks to study subjects. This includes testing to ensure analytical methods produce reliable and valid data throughout the course of the study. This can also include, but is not limited to, investigation of unexpected results, incurred sample reanalysis, and analyses for method transfer and comparability.

All samples and associated results will be coded prior to being shipped from the site for analysis or storage. Samples will be tracked using a unique identifier that is assigned to the samples for the study. Results are stored in a secure database to ensure confidentiality.

When permitted by local regulations and if informed consent is provided by the subject, Amgen can do additional testing on remaining samples (ie, residual and back-up) to investigate and better understand the small cell lung cancer, the dose response and/or prediction of response to Amgen investigational product(s) or other protocol-specified therapy, characterize antibody response, and characterize aspects of the molecule (eg, mechanism of action/target, metabolites). Results from this analysis are to be documented and maintained but are not necessarily reported as part of this study. Samples can be retained for up to 20 years.

Since the evaluations are not expected to benefit the subject directly or to alter the treatment course, the results of pharmacogenetic, biomarker development or other exploratory studies are not placed in the subject's medical record and are not to be made available to the subject, members of the family, the personal physician, or other third parties, except as specified in the informed consent.

The subject retains the right to request that the sample material be destroyed by contacting the investigator. Following the request from the subject, the investigator is to provide the sponsor with the required study and subject number so that any remaining sample types (eg, blood, tumor) samples and any other components from the cells can be located and destroyed. Samples will be destroyed once all protocol-defined procedures are completed. However, information collected from samples prior to the request for destruction, will be retained by Amgen.

Protocol Number: 20200439

Date: 05 June 2024 Page 152 of 176

The sponsor is the exclusive owner of any data, discoveries, or derivative materials from the sample materials and is responsible for the destruction of the sample(s) at the request of the subject through the investigator, at the end of the storage period, or as appropriate (eg, the scientific rationale for experimentation with a certain sample type no longer justifies keeping the sample). If a commercial product is developed from this research project, the sponsor owns the commercial product. The subject has no commercial rights to such product and has no commercial rights to the data, information, discoveries, or derivative materials gained or produced from the sample. See Section 11.3 for subject confidentiality.

Protocol Number: 20200439

Date: 05 June 2024 Page 153 of 176

11.7 Appendix 7. Hepatotoxicity Stopping Rules: Suggested Actions and Follow-up Assessments and Study Treatment Rechallenge Guidelines

Subjects with abnormal hepatic laboratory values (ie, alkaline phosphatase [ALP], aspartate aminotransferase [AST], alanine aminotransferase [ALT], total bilirubin [TBL]) and/or international normalized ratio (INR) and/or signs/symptoms of hepatitis (as described below) may meet the criteria for withholding or permanent discontinuation of Amgen investigational product or other protocol-required therapies, as specified in the *Guidance for Industry Drug-Induced Liver Injury: Premarketing Clinical Evaluation, July 2009.*

Criteria for Withholding and/or Permanent Discontinuation of Amgen Investigational Product and Other Protocol-required Therapies Due to Potential Hepatotoxicity

The following stopping and/or withholding rules apply to subjects for whom another cause of their changes in liver biomarkers (TBL, INR and transaminases) has not been identified.

Important alternative causes for elevated AST/ALT and/or TBL values include, but are not limited to:

- Hepatobiliary tract disease
- Viral hepatitis (eg, hepatitis A/B/C/D/E, Epstein-Barr Virus, cytomegalovirus, herpes simplex virus, varicella, toxoplasmosis, and parvovirus)
- Right sided heart failure, hypotension or any cause of hypoxia to the liver causing ischemia
- Exposure to hepatotoxic agents/drugs or hepatotoxins, including herbal and dietary supplements, plants and mushrooms
- Heritable disorders causing impaired glucuronidation (eg, Gilbert's syndrome, Crigler-Najjar syndrome) and drugs that inhibit bilirubin glucuronidation (eg, indinavir, atazanavir)
- Alpha-one antitrypsin deficiency
- Alcoholic hepatitis
- Autoimmune hepatitis
- Wilson's disease and hemochromatosis
- Nonalcoholic fatty liver disease including steatohepatitis
- Non-hepatic causes (eg, rhabdomyolysis, hemolysis)

Protocol Number: 20200439

Date: 05 June 2024 Page 154 of 176

If investigational product(s) is/are withheld, the subject is to be followed for possible drug induced liver injury (DILI) according to recommendations in the last section of this appendix.

Rechallenge may be considered if an alternative cause for impaired liver tests (ALT, AST, ALP) and/or elevated TBL, is discovered and the laboratory abnormalities resolve to normal or baseline (see next section in this appendix).

Table 11-3. Conditions for Withholding and/or Permanent Discontinuation of Amgen Investigational Product and Other Protocol-required Therapies Due to Potential Hepatotoxicity

Analyte	Temporary Withholding	Permanent Discontinuation
TBL	> 3 x ULN at any time	> 2 x ULN
		OR
INR		> 1.5 x (for subjects not on anticoagulation therapy)
	OR	AND
AST/ALT	> 8 x ULN at any time > 5 x ULN but < 8 x ULN for ≥ 2 weeks > 5 x ULN but < 8 x ULN and unable to adhere to enhanced monitoring schedule > 3 x ULN with clinical signs or symptoms that are consistent with hepatitis (such as right upper quadrant pain/tenderness, fever, nausea, vomiting, and jaundice) OR	In the presence of no important alternative causes for elevated AST/ALT and/or TBL values > 3 x ULN (when baseline was < ULN)
ALP	> 8 x ULN at any time	

ALP = alkaline phosphatase; ALT = alanine aminotransferase; AST = aspartate aminotransferase; INR = international normalized ratio; TBL = total bilirubin; ULN = upper limit of normal

Criteria for Rechallenge of Amgen Investigational Product and Other Protocol-required Therapies After Potential Hepatotoxicity

The decision to rechallenge the subject is to be discussed and agreed upon unanimously by the subject, investigator, and Amgen.

If signs or symptoms recur with rechallenge, then tarlatamab and other protocol-required therapies are to be permanently discontinued. Subjects who clearly meet the criteria for permanent discontinuation (as described in Table 11-3) are never to be rechallenged.

Protocol Number: 20200439

Date: 05 June 2024 Page 155 of 176

Drug-induced Liver Injury Reporting and Additional Assessments

Reporting

To facilitate appropriate monitoring for signals of DILI, cases of concurrent AST or ALT and TBL and/or INR elevation, according to the criteria specified in the above, require the following:

- The event is to be reported to Amgen as a serious adverse event immediately and no later than 24 hours of discovery or notification of the event (ie, before additional etiologic investigations have been concluded)
- The appropriate case report form (CRF) (eg, Events CRF) that captures information necessary to facilitate the evaluation of treatment-emergent liver abnormalities is to be completed and sent to Amgen

Other events of hepatotoxicity and potential DILI are to be reported as serious adverse events if they meet the criteria for a serious adverse event defined in Section 11.4.

Additional Clinical Assessments and Observation

All subjects in whom investigational product(s) or protocol-required therapies is/are withheld (either permanently or conditionally) due to potential DILI as specified in Table 11-3 or who experience AST or ALT elevations > 3 x upper limit of normal (ULN) or 2-fold increases above baseline values for subjects with elevated values before drug are to undergo a period of "close observation" until abnormalities return to normal or to the subject's baseline levels.

Assessments that are to be performed during this period include:

- Repeat AST, ALT, ALP, bilirubin (BIL) (total and direct), and INR within 24 hours
- In cases of TBL > 2x ULN or INR > 1.5, retesting of liver tests, BIL (total and direct), and INR is to be performed every 24 hours until laboratory abnormalities improve

Testing frequency of the above laboratory tests may decrease if the abnormalities stabilize or the investigational product(s) or protocol-required therapies has/have been discontinued AND the subject is asymptomatic.

Initiate investigation of alternative causes for elevated AST or ALT and/or elevated TBL. The following are to be considered depending on the clinical situation:

- Complete blood count with differential to assess for eosinophilia
- Serum total immunoglobulin (Ig)G, anti-nuclear antibody anti-smooth muscle antibody, and liver kidney microsomal antibody-1 to assess for autoimmune hepatitis
- Serum acetaminophen (paracetamol) levels

Protocol Number: 20200439

Date: 05 June 2024 Page 156 of 176

- A more detailed history of:
 - Prior and/or concurrent diseases or illness
 - Exposure to environmental and/or industrial chemical agents
 - Symptoms (if applicable) including right upper quadrant pain,
 hypersensitivity-type reactions, fatigue, nausea, vomiting and fever
 - o Prior and/or concurrent use of alcohol, recreational drugs and special diets
 - Concomitant use of medications (including non-prescription medicines and herbal and dietary supplements), plants, and mushrooms
- Viral serologies
- Creatine phosphokinase, haptoglobin, lactate dehydrogenase (LDH), and peripheral blood smear
- Appropriate liver imaging if clinically indicated
- Appropriate blood sampling for PK analysis if this has not already been collected
- Hepatology consult (liver biopsy may be considered in consultation with a hepatologist)

Follow the subject and the laboratory tests (ALT, AST, TBL, INR) until all laboratory abnormalities return to baseline or normal or considered stable by the investigator. The "close observation period" is to continue for a minimum of 4 weeks after discontinuation of all investigational product(s) and protocol-required therapies.

The potential DILI event and additional information such as medical history, concomitant medications and laboratory results must be captured in the corresponding CRFs.

Protocol Number: 20200439

Date: 05 June 2024 Page 157 of 176

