5.1 Inclusion Criteria

Subjects are eligible to be included in the study only if all the following criteria apply:

- Subject has provided informed consent prior to initiation of any study specific activities/procedures.
- 102 Age ≥ 18 years.
- Subjects with histologically or cytologically confirmed SCLC who progressed or recurred following at least 1 platinum-based regimen

Note: In countries where standard of care first line systemic treatment includes platinum containing chemotherapy in combination with PD-L1 inhibitor, it is required that patients have failed PD-L1 inhibitor therapy as part of their first systemic treatment or have no access to PD-L1 inhibitors.

Note: If patients progress or relapse within 6 months from receiving platinum containing-systemic treatment for limited stage disease, they are eligible for study regardless of receiving PD-L1 containing regimen.

Note: Subjects with a diagnosis of combined small cell carcinoma with predominant small cells (as determined by the local pathologist) may be

[figure not shown]

Protocol Number: 20200439

Date: 05 June 2024 Page 49 of 176

considered for inclusion based on investigator discretion and after discussion with the medical monitor.

- Subjects with disease measurable by modified Response Evaluation Criteria in Solid Tumors (RECIST) 1.1
- Subjects with treated brain metastases are eligible provided they meet the following criteria:

- 106 Eastern Cooperative Oncology Group (ECOG) 0 to 1
- 107 Adequate organ function per local laboratory, defined as follows:
 - absolute neutrophil count ≥ 1 x 10⁹/L
 - platelet count ≥ 75 x 10⁹/L
 - hemoglobin > 9 g/dL (90 g/L)
 - Estimated glomerular filtration rate based on Modification of Diet in Renal Disease (MDRD) calculation > 45 mL/min/1.73 m²
 - aspartate aminotransferase (AST) and alanine aminotransferase (ALT)
 3 x upper limit of normal (ULN) (or < 5 x ULN for subjects with liver involvement).
 - total bilirubin (TBL) < 1.5 x ULN (or < 2 x ULN for subjects with liver metastases).
 - Prothrombin time (PT)/international normalized ratio (INR) and partial thromboplastin time (PTT) or activated partial thromboplastin time (aPTT)
 ≤ 1.5 x institutional ULN (subjects on stable anticoagulation are permitted)
- 108 Pulmonary function:
 - No clinically significant pleural effusion. Treatment of pleural effusions to meet eligibility is permitted.
 - Baseline oxygen saturation > 90% on room air
- 109 Cardiac function:
 - Cardiac ejection fraction ≥ 50%,

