9.6.3 Laboratory Test Results

The analyses of safety laboratory endpoints will include summary statistics at selected time points by cohort. Shifts in grades of safety laboratory values between the baseline and the worst on-study value will be tabulated by cohort.

Summaries of the absolute value and/or changes from baseline at each scheduled assessment will be provided for selected laboratory parameters of interest.

Shift tables indicating the change between the baseline and the maximum post dose CTCAE grades for an increased value, and the maximum post dose grade for a decreased value will be provided for selected laboratory parameters of interest.

Unscheduled assessments will be included in the shift tables.

Potential Hy's law cases will be listed and may also be summarized by cohort. Hy's law cases will have the following three components: 1) ALT or AST > 3 X ULN, 2) ALP < 2 X ULN and 3) TB >2 X ULN, on any day. A listing of AST, ALT and Total Bilirubin values at each time point will be produced for the subjects suspected of Hy's law case.

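### Table 11-3 has no combined AST/ALT-plus-bilirubin (or INR) rule for subjects entering with AST/ALT at or above ULN, so a narrow zone carries no required tarlatamab hold

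*Protocol*

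**What the plan says.** Table 11-3 (Protocol Section 11.7, Appendix 7) has a single permanent-discontinuation criterion. Bilirubin must exceed 2 x ULN, or INR must exceed 1.5 ("for subjects not on anticoagulation therapy"). In addition AST/ALT must be "> 3 x ULN (when baseline was < ULN", with no important alternative cause. The consequence is final: "Subjects who clearly meet the criteria for permanent discontinuation (as described in Table 11-3) are never to be rechallenged".

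The temporary-withholding column has no baseline limit. Any one of these is enough:
- bilirubin > 3 x ULN;
- AST/ALT > 8 x ULN;
- AST/ALT "> 5 x ULN but < 8 x ULN for ≥ 2 weeks", or in that range when enhanced monitoring cannot be kept up;
- AST/ALT > 3 x ULN with clinical signs or symptoms of hepatitis, jaundice being one of the listed examples;
- ALP > 8 x ULN.

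This column has no INR entry.

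Inclusion criterion 107 (Section 5.1) admits AST/ALT up to 3 x ULN ("or < 5 x ULN for subjects with liver involvement"). On coagulation it adds that "subjects on stable anticoagulation are permitted".

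SAP Section 9.6.3 defines a potential Hy's law case by "ALT or AST > 3 X ULN, 2) ALP < 2 X ULN and 3) TB >2 X ULN, on any day", whatever the baseline.

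**The concern.** The combined criterion is the only place where Table 11-3 acts on AST/ALT and bilirubin (or INR) together at levels that neither would trigger alone. It switches off for every subject whose baseline AST/ALT was at or above ULN, including those just over the limit and those with liver involvement whom the trial chose to admit. If nothing else requires a hold, two subjects with the same unexplained liver values can receive opposite instructions because their baselines fall on either side of ULN. The SAP would list both as potential Hy's law cases if ALP is < 2 x ULN, yet the protocol would let the next tarlatamab dose go ahead in one of them.

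**Working it through.** The plan gives no figure to reproduce, so the check reads the rules as logic.

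**Step 1: Table 11-3 as rules** (no alternative cause found; B = baseline AST/ALT, A = on-study AST/ALT, T = bilirubin, all in multiples of ULN):
- Permanent stop: (T > 2, or INR > 1.5 off anticoagulation) and A > 3 and B < 1.
- Hold: T > 3; or A > 8; or 5 < A < 8 for at least 2 weeks or unmonitored; or A > 3 with signs or symptoms; or ALP > 8.

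**Step 2: a matched pair.** Take A = 4, T = 2.5, normal INR and ALP, no signs or symptoms, one week's duration.
- B = 0.9 (a 4/0.9 = 4.4-fold rise): permanent stop.
- B = 1.1 (a 4/1.1 = 3.6-fold rise): no stop and no hold.

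**Step 3: the same check over a range.** With A at 3.1, 4, 5, 5.1 and 7.9 and T at 2.1, 2.5 and 3.0 there are 5 x 3 = 15 combinations.
- At B = 0.9, all 15 give a permanent stop.
- At B = 1.0, 1.5, 2.9 and 4.5, all 4 x 15 = 60 give no required action. Some of these are not a rise at all (for example B = 4.5 with A = 4), so the count tests the logic and says nothing about frequency.
- A hold returns with signs or symptoms, T = 3.1, A = 9, A = 6 for 2 weeks, or A = 6 unmonitored.
- INR appears only in the permanent column, tied to the same baseline limit. At B at or above 1, INR > 1.5 off anticoagulation with T at 3 or less therefore adds nothing.

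**Step 4: other rules that might fill the gap.**
- Section 6.2.2.1.3 withholds for a DLT, for symptomatic hypophysitis, or for the Section 11.7 conditions themselves. Its no-restart items need grade 4 or higher, or grade 3 that recurs or has not recovered in 3 weeks.
- Table 6-2 has a combined rule without a baseline limit (AST/ALT > 3 x with bilirubin > 1.5 x), but it governs AMG 404. It reaches tarlatamab only through the DLT definition in Section 6.2.1.4, inside the DLT window. Table 6-1 says AMG 404 is no longer supplied as of Amendment 3.
- Table 6-4 applies if the event is managed as CRS.
- Sections 7 and 7.1 allow the investigator or sponsor to stop treatment but do not require it.
- Appendix 7 requires close observation: repeat tests within 24 hours, retesting every 24 hours while bilirubin is > 2 x ULN or INR > 1.5, and a search for other causes. None of this is a hold.

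**Step 5: reporting.** The 24-hour DILI report covers "cases of concurrent AST or ALT and TBL and/or INR elevation, according to the criteria specified in the above". It is unclear whether that reaches a case outside the permanent-stop criterion. Other hepatotoxicity is reported as serious if it meets the general seriousness criteria.

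**Step 6: what a 2-fold-over-baseline condition would catch.** The AST/ALT threshold is max(3, 2B):

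| Baseline (x ULN) | Threshold (x ULN) | Part of the 3 to 8 x band covered |
|---|---|---|
| 1.0 to 1.5 | 3 | all |
| 2.0 | 4 | 4 to 8 x |
| 3.0 | 6 | 6 to 8 x |
| 4.0 | 8 | none below 8 x |
| 4.5 | 9 | none |

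**The case against.** The strongest reply is that the baseline limit is deliberate. A subject with liver involvement may enter with AST/ALT between 3 and 5 x ULN and would meet an unrestricted > 3 x limb on day 1. This stands, and a reader should not infer that the limit is a drafting error. It explains why a flat 3 x threshold does not suit high baselines. It does not explain exempting a baseline of 1.1 x, or leaving out any relative threshold.

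A second reply is that few people are exposed. Section 4.1 says enrollment ended in January 2023 and this protocol version is dated 05 June 2024, so anyone still dosed entered at least 16 months earlier. Several conditions must also coincide. This stands too and limits the importance of the point.

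Third, the > 5 to < 8 x band nearly closes itself. A hold starts at 2 weeks, and Table 1-2 shows tarlatamab in weeks 1 and 3, so about one dose is exposed. Table 6-2 grades AST/ALT of 5 to 20 x as grade 3, and the 3-week recovery rule in Section 6.2.2.1.3 presupposes some interruption for grade 3 events. The gap is therefore least secure in this band. The > 3 to 5 x band is unaffected.

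Fourth, the hold for AST/ALT > 3 x responds to signs as well as symptoms. A subject who feels well but is visibly jaundiced is already held, so part of the bilirubin > 2 to 3 x range is covered in practice.

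**Conclusion.** The gap exists on the text, under all of the following conditions: baseline AST/ALT at or above ULN; outside the DLT window; a first unexplained episode; no clinical signs or symptoms of hepatitis, jaundice included; and not managed as CRS. The values concerned are AST/ALT > 3 to 5 x ULN, or > 5 to < 8 x for under 2 weeks with monitoring. They must be combined with bilirubin > 2 to 3 x ULN, or with INR > 1.5 off anticoagulation and bilirubin 3 x or less.

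A reader might infer that subjects with raised baselines have no liver safeguards. The documents do not support that: every temporary hold applies to them, and close observation is mandatory. A reader might also infer that the permanent stop must be extended to them. That is a clinical trade-off in a group that includes subjects with liver metastases, and the text does not settle it. What is missing is a required pause while the cause is sought.

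The number of subjects still on tarlatamab and the share with raised baselines are not given; that they are few is inferred from the enrollment date. I would class this as a cheap improvement.

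**What to change.** Add one condition to the temporary-withholding column of Table 11-3 for baseline AST/ALT at or above ULN: AST/ALT > 3 x ULN and at least 2 x baseline, with bilirubin > 2 x ULN or INR > 1.5 (not on anticoagulation), and no important alternative cause. The action is to withhold tarlatamab pending work-up. Permanent discontinuation is left to the sponsor's safety physicians. The 2-fold multiple is the one Appendix 7 already uses to start close observation when values were raised before treatment. Add a phrase to the DILI reporting paragraph stating that the 24-hour serious adverse event report covers this condition.

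The condition does not close everything. Cover shrinks as baseline rises and is nil from 4 x ULN. For example, a subject going from 4.5 x to 7.9 x with bilirubin 2.9 x for under 2 weeks would still not be held, because the condition would need 9 x. Nor would a subject who stays at 4.5 x while bilirubin reaches 2.1 x. If the safety physicians want those cases held, they need a different rule.

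The cost is one table entry and one phrase, with no extra tests or patients. The downside is an occasional missed dose in a subject with a raised baseline.

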Appendix 8. Performance Status According to Eastern Cooperative Oncology Group (ECOG) 11.8

	ECOG Performance Status Scale
Grade	Descriptions
0	Fully active, able to carry on all pre-disease performance without restriction
1	Restricted in physically strenuous activity but ambulatory and able to carry out work of a light or sedentary nature, eg, light house work, office work
2	Ambulatory and capable of all selfcare but unable to carry out any work activities. Up and about more than 50% of waking hours
3	Capable of only limited selfcare, confined to bed or chair more than 50% of waking hours
4	Completely disabled. Cannot carry on any selfcare. Totally confined to bed or chair
5	Dead

ECOG = Eastern Cooperative Oncology Group. Source: Oken et al, 1982

Protocol Number: 20200439

Date: 05 June 2024 Page 158 of 176

11.9 Appendix 9. Modified Response Evaluation Criteria in Solid Tumors Version 1.1 (Modified RECIST 1.1)

Response Evaluation Criteria in Solid Tumors version 1.1 (RECIST 1.1) are guidelines for assessing tumor burden changes in response to treatment (Eisenhauer et al, 2009). Additional patterns of response have been observed with immune-enhancing therapies, including delayed clinical response, leading to criteria modifications to capture treatment responses more accurately (Nishino et al, 2013; Wolchok et al, 2009). This study utilizes modified RECIST 1.1 criteria which applies aspects of the immune-related response criteria (including requiring confirmation of disease progression) to RECIST 1.1 as outlined below.

Modified RECIST 1.1 tumor response assessment

 All measurable and non-measurable lesions should be assessed at screening, all defined tumor assessment time points (Schedule of Assessment), and any unscheduled imaging visits.

Measurable lesions:

- Non-nodal lesions with clear borders that can be measured accurately and serially in one dimension in the axial plane (longest diameter ≥ 10 mm measured by magnetic resonance imaging/computed tomography [MRI/CT] with scan slice thickness ≤ 5 mm).
- Nodal lesions with the longest diameter perpendicular to the long axis (short axis)
 ≥ 15 mm on MRI/CT.
- Must exclude simple cysts, pleural/pericardial effusions and ascites.

Non-measurable lesions:

- All other lesions, including small lesions (longest diameter < 10 mm or pathological lymph nodes with ≥ 10 mm but < 15 mm short axis) are considered non-measurable and characterized as non-index lesions.
- Other examples of non-measurable lesions include:
 - Lesions with prior local treatment:
 - Tumor lesions situated in a previously irradiated area, or an area subject to other loco-regional therapy, should not be considered measurable unless there has been demonstrated progression in the lesion.
 - Biopsied lesions
 - Categorically, clusters of small lesions, bone lesions, inflammatory breast disease, and leptomeningeal disease are non-measurable. See Imaging Procedural Manual provided by the central imaging core laboratory for additional guidance.

Protocol Number: 20200439

Date: 05 June 2024 Page 159 of 176

Index lesions and measurable tumor burden:

Index lesions:

- Measurable lesions (≤ 5 lesions per organ, ≤ 10 total) selected at baseline on the basis of
 - Size and suitability for accurate repeated measurements by imaging.
 - Representative of the subject's tumor burden, all organs involved and overall disease status

Non-index lesions:

- All measurable lesions not selected as index lesions and non-measurable lesions
- Non-index lesions will be qualitatively evaluated
 - Values: 'Present', 'absent' or 'unequivocal progression'.
- Other definitions
 - Unable to evaluate (UE): Any lesion present at baseline which was not assessed or was unable to be evaluated leading to an inability to determine the status of that particular tumor for that time point
 - Not Available (NA): Scan not available
 - Not Done (ND): Radiologic imaging was not performed at this time point to evaluate the index lesions

Index lesion response:

- At baseline and all subsequent tumor assessments, measurable tumor burden is the sum of the longest diameters (SLD) of all index lesions
- Complete Response (CR) disappearance of all measurable lesions
 - Pathologic lymph nodes must have reduction in short axis to < 10 mm
- Partial Response (PR) decrease of 30% or greater in tumor burden compared with baseline
- Stable Disease (SD) not meeting the criteria for CR, PR, or progressive disease
- Progressive Disease increase of 20% or greater in tumor burden compared with nadir, or the appearance of one or more new lesions

Non-index lesion response:

- CR disappearance of all non-index lesions
 - Pathologic lymph nodes must have reduction in short axis to < 10 mm
- SD persistence of one or more non-index lesions, not meeting the criteria for CR or progressive disease
- Progressive disease unequivocal progression of existing non-index lesions, or the appearance of one or more new lesions

Protocol Number: 20200439

Date: 05 June 2024 Page 160 of 176

Overall response:

CR

- Complete disappearance of all lesions
 - Pathologic lymph nodes must have reduction in short axis to
 10 mm
- Confirmation scan required repeat, consecutive assessment no less than 4 weeks from the date of the first documented response
- o CR is dated at time of confirmation scan
- PR
- Decrease in tumor burden ≥ 30% relative to baseline, or
- Complete disappearance of all index lesions with presence of non-index lesions
- Confirmation scan required repeat, consecutive assessment no less than 4 weeks from the date of the first documented response
- o PR is dated at time of confirmation scan
- SD
- o Index lesions not meeting criteria for CR, PR or progressive disease, or
- In subjects with only non-index disease, persistence of one or more non-index lesions
- Progressive Disease
 - Radiologic detection of ≥ 20% increase in tumor burden relative to nadir and at least 5 mm absolute increase, or
 - Unequivocal progression of non-index lesions, or
 - The presence of new lesions
 - Confirmation scan required repeat, consecutive assessment from the date of the first documented response
 - Radiographic progressive disease is confirmed at repeat imaging

it:

- Tumor burden remains increased by ≥ 20% and at least
 5 mm absolute increase relative to nadir, or
- Unequivocal progression of non-index lesions is observed, or
- New lesions are present
- Subjects with a global deterioration of health status requiring discontinuation of treatment prior to radiologic confirmation of disease progression should have the reason for treatment discontinuation classified as 'clinical disease progression' not 'radiographic progressive disease'. Every effort should be made to radiologically confirm progression even after discontinuation of treatment.

Protocol Number: 20200439

Date: 05 June 2024 Page 161 of 176

Summary of Measure	men	t and Tumor Respo RECIST 1.		ent Based on Modified									
Measurable lesions		 Non-nodal lesion measurement) Pathologic lympi ≥ 15 mm 		nidimensional est diameter short axis									
Measurement of each lesion		Non-nodal lesion planePathologic lymp	_	t diameter (mm) in the axial axis (mm)									
Tumor burden		Sum of the longUp to 5 lesions p	•	SLD) of all index lesions o 10 total									
Response assessment: index lesions (calculated from % chan in tumor burden)	ge	 CR: Disappearance of all lesions Pathologic lymph nodes short axis < 10 mm PR: ≥ 30% decrease from baseline SD: Does not meet criteria for CR, PR or progressive disease. Progressive disease: ≥ 20% increase (and ≥ 5 mm absolute increase) from nadir 											
Response assessment: non-index lesions		 CR: Disappearance of all lesions Pathologic lymph nodes short axis < 10 mm SD: Persistence of one or more non-index lesion(s) Progressive disease: Unequivocal progression of existing non-index lesions 											
New Lesions		The presence of new lesion(s) defines progression											
Confirmation		Confirmation by su required for CR, P	•	essment after ≥4 weeks ssive disease.									
Summary of N	Modi	fied RECIST 1.1 Ov	erall Respons	e Assessment									
Index lesions (tumor burden) ^a , %	No	n-Index lesions	New lesions	Overall Response using modified RECIST 1.1									
↓ 100%	Ab	sent	Absent	CR ^b									
Noned	Ab	sent	Absent	CR⁵									
↓ 100%	Pre	esent	Absent	PR^b									
↓≥30 %	Ab	sent/Present	Absent	PR^{b}									
↓ < 30% to ↑ < 20%	Ab	sent/Present	Absent	SD									
Noned	Pre	esent	Absent	SD									
↑≥ 20%	An	У	Any	Progressive disease ^c									
Any		equivocal gression	Any	Progressive disease ^c									
Any	An	y	Present	Progressive disease ^c									
NA/ND/UE	Ab	sent/Present	Absent	UE									
Noned	NA	/ND/UE	ND/UE Absent										

CR = complete response; NA = not available; ND = not done; PR = partial response; RECIST = Response Evaluation Criteria in Solid Tumors; **SD = stable disease;** UE = unable to evaluate

^a Decrease assessed relative to baseline. Increase assessed relative to nadir.

^b Response: CR and PR require a confirmation assessment after ≥ 4 weeks, may also wait until the next scheduled imaging

^c Progression: Progressive disease requires a confirmation assessment

^d Subjects with non-index lesions only

Protocol Number: 20200439

Date: 05 June 2024 Page 162 of 176

11.10 Appendix 10. Schedule of Activities:

Table 11-4. List of Schedule of Activities Tables

Quick link to Schedule of Activities	Table Title
Table 11-5	One-Step Dosing – Cycle 1 only (AMG 404 Administered
Table 11-6	One-Step Dosing – Cycle 1 only (AMG 404 Administered
Table 11-7	One-Step Dosing – Cycle 1 only (AMG 404 Administered
Table 11-8	Cycle 2 and Beyond (AMG 404 Administered on in Cycle 1)
Table 11-9	Cycle 2 and Beyond (AMG 404 Administered on in Cycle 1)

Protocol Number: 20200439

Date: 05 June 2024 Page 163 of 176

Table 11-5. Schedule of Activities: One-Step Dosing – Cycle 1 Only (AMG 404 Administered

STUDY PERIOD/ **TREATMENT CYCLE SCR**^a Cycle 1 only -3 WEEK^b to -1 DAYb **EOI 404** Pre 404 EOI 757 EOI 757 EOI 757 **Pre 757** Pre 757 48 N N **HOUR** (relative to infusion)d General/Safety Assessments Informed consent Χ Clinical Evaluatione Χ Χ Х Χ Χ Х Χ Х Χ Χ Χ Х Vital signs, pulse Х Χ Χ Х \mathbf{X}^{f} Χ Χ X^f Χ X^f Χ Χ Χ Χ Χ oxf 12-lead ECG⁹ Χ Χ Χ Χ Χ ECHO or MUGA Х Adverse event review Serious adverse event review Prior/concomitant medication Local Laboratory Assessments CBC with Χ Χ Χ Χ Χ Χ Χ Χ Χ Χ Χ Χ differential Coagulation Χ Х Х Χ Χ Х Х Х Chemistry panelh Х Χ Χ Χ Χ Χ Χ Χ Χ Х Х Χ Х Lipase and Χ Χ Amylase Urinalysis Х Serum/urine Х Χ pregnancy testi Safety endocrine Х panel^j CRP Χ Χ Х Χ Χ Х Х Х Х Χ Χ Χ Ferritin Χ Χ Х Χ Χ Х Χ Χ Χ Х Χ Χ HBsAg, HBcAb, Х HCV Ab, HIV

AMGEN®

Page 1 of 3

Protocol Number: 20200439

Date: **05 June 2024** Page 164 of 176

Table 11-5. Schedule of Activities: One-Step Dosing – Cycle 1 Only (AMG 404 Administered

STUDY PERIOD/ **TREATMENT CYCLE** SCR^a Cycle 1 only -3 to -1 WEEK^b DAYb EOI 757 Pre 404 EOI 404 Pre 757 EOI 757 Pre 757 Pre 757 EOI 757 24 48 24 24 48 N စ N 6 HOUR (relative to infusion)d Central and Biomarker Laboratory Tests

Study Drug Administration

Tarlatamab IV infusion^t AMG 404 IV

infusion^t

Protocol Number: 20200439

Date: 05 June 2024 Page 165 of 176

Table 11-5. Schedule of Activities: One-Step Dosing – Cycle 1 Only (AMG 404 Administered

STUDY PERIOD/ TREATMENT																							
CYCLE	SCRª											Cyc	le 1 o	nly									
WEEK ^b	-3 to -1					1							2	2					3				4
DAY ^b																							
		Pre 4	EOI 404	Pre 7	EOI 757	2	6	24	48	96	Pre 757	EOI 757	2	စ	24	48	Pre 757	EOI 7	2	6	24	48	168
HOUR (relative to infusion) ^d		404	04	757	57						57	57					57	757					
Study Drug Administr	ation (contin	ued)																					
Dexamethasone or equivalent ^u				Х							Х						X						
IV Hydration ^v					Χ							Χ						Х					
Hospital stay ^w		←==	====			=====		===→			+ ==	=====	=====	=====	== →		←====		=====	=====	===→		
Other Assessments																							
MRI Brain ^x	X																						
Radiological																							
imaging and tumor burden assessment ^y	Х																						

Page 3 of 3

Protocol Number: 20200439

Date: 05 June 2024 Page 166 of 176

Table 11-6. Schedule of Activities: One-Step Dosing – Cycle 1 Only (AMG 404 Administered

STUDY PERIOD/ **TREATMENT SCR**^a CYCLE Cycle 1 only WEEK^b to -1 DAYb **EOI 757 EOI 404** Pre 757 **EOI 757 EOI 757** Pre 404 168 24 48 24 8 24 တ N 6 N **HOUR** (relative to infusion)d General/Safety Assessments Informed consent Χ Clinical Evaluatione Х Χ Χ Х Х Х Χ Χ Vital signs, pulse Х Χ Χ X^f Х Χ Х Χ X^f Χ Х Χ X^f Χ Χ ox^f 12-lead ECG⁹ Χ Χ Χ Χ Χ ECHO or MUGA Х Adverse event review Serious adverse event review Prior/concomitant medication **Local Laboratory Assessments** CBC with Χ Χ Х Χ Χ Χ Χ Χ Х Χ Χ Χ differential Coagulation Х Χ Χ Χ Χ Х Х Х Chemistry panelh Χ Х Χ Χ Х Χ Х Х Χ Χ Lipase and Х Χ Amylase Urinalysis Х Serum/urine Х Χ pregnancy Testi Safety endocrine Х panel^j CRP Х Χ Χ Χ Χ Χ Χ Χ Χ Χ Χ Χ Х Ferritin Χ X Χ X Χ Х X Χ Х Χ Χ Χ Χ HBsAg, HBcAb, Х HCV Ab, HIV Central and Biomarker Laboratory Tests

Footnotes described after Table 11-9

AMGEN

Protocol Number: 20200439

Date: 05 June 2024 Page 167 of 176

Table 11-6. Schedule of Activities: One-Step Dosing – Cycle 1 Only (AMG 404 Administered Day 8)

	4510 11								 		ə			 	(, ,,,,,,,,,,,,,,,,,,,,,,,,,,,,,,,,,,,,						-,		
STUDY PERIOD/ TREATMENT																							
CYCLE	SCR ^a											Cy	cle 1	only									
WEEK ^b	-3 to -1				1								2 ^c							3			4
VVEEN	to -1				1							4	 							3			4
DAY ^b																							
		70	_						70	m	-	m					п	m					
		Pre:	Ö	N	၈	24	48	96	e'	0	re	0	2	၈	24	48	re	EOI 757	2	ြ	24	48	168
HOUR (relative to infusion) ^d		757	EOI 757			_			Pre 404	EOI 404	Pre 757	EOI 757			_		Pre 757	757			_		 
	er Laborator	y Test	ts (cont	tinued)				1										ı		ı			
	ral and Biomarker Laboratory Tests (continued)																						
Study Drug Administr	ration																						
arlatamab IV																							
nfusion ^t																							
AMG 404 IV																							
nfusion ^t																							
Dexamethasone or			1															1	1				
equivalent ^u		Х									Х						Х						
IV Hydration ^v		1	Х					1	1	1		Х		1	 			Х					
		+			  =====		1	1		 	 		1			 	-		 	1			
Hospital stay ^w			=====	=====										=====	==→		— ==	=====			:==→		

Protocol Number: 20200439

Date: **05 June 2024** Page 168 of 176

Table 11-6. Schedule of Activities: One-Step Dosing – Cycle 1 Only (AMG 404 Administered Day 8)

STUDY PERIOD/ TREATMENT CYCLE	SCR ^a											Cy	/cle 1	only									
	-3																						
